Currently, the most reliable tool for diagnosing preload dependence is a dynamic test: passive leg raise (supine) or Trendelenburg (prone) with continuous cardiac output monitoring. A $\geq 10\%$ increase in cardiac output indicates preload dependence. Studies, including work by our team, confirm sensitivity and specificity $>85\%$. This test performs well to identify patient who are preload-dependent, and who are consequently at higher risk of preload-dependent hypotension. Yet, in preload-independent patients (i.e. those with a negative passive leg raising test, no validated predictive test exists for ultrafiltration-related hypotension in relation with their switch to a preload-dependent status.

Research Hypothesis

A 250 mL rapid ultrafiltration challenge (15 or 30 minutes) may help identify preload-independent patients at risk of becoming preload dependent during CRRT

Justification of Methodological Choices

- Sequential crossover design: each patient serves as their own control, limiting variability.
- Randomization of challenge order prevents bias.
- 250 mL volume chosen as it mimics passive leg raise (~300 mL).
- Two rates (15 vs. 30 minutes) tested to assess the effect of ultrafiltration kinetics and plasma refilling.

The PiCCO® Monitoring Device

The device combines transpulmonary thermodilution and pulse contour analysis for continuous cardiac output and displays advanced hemodynamic parameters (extravascular lung water, pulmonary vascular permeability index, global end-diastolic volume index).

Benefit/Risk Assessment

- Benefit: collective, through validation of a new predictive test.
- Risk: minimal, transient hemodynamic instability possible
- No additional invasive procedures required.

Expected Outcomes

A UF challenge may have higher diagnostic performance than the passive leg raising test to identify patients at the transition between preload independence and dependence. It is simple, dynamic, inexpensive, and potentially useful in guiding ultrafiltration in CRRT patients.

RESEARCH OBJECTIVES

Primary Objective

To evaluate the diagnostic performance of a rapid ultrafiltration challenge (250 mL over 15 or 30 minutes) in detecting preload dependence in preload independent critically ill patients treated with continuous renal replacement therapy.

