Diagnostic accuracy will be assessed by the change in calibrated cardiac index induced by the ultrafiltration challenge compared with the reference postural maneuver (passive leg raise or Trendelenburg) performed *after* the challenge.

Secondary Objectives

1. To evaluate separately the diagnostic performance of the 15-minute and 30-minute UF challenges.
2. To determine the optimal threshold of calibrated cardiac index variation defining preload dependence for each test (pooled and separate), with sensitivity, specificity, PPV, and NPV.
3. To compare diagnostic performance of UF challenges (pooled and separate) with that of the pre-test postural maneuver.
4. To compare diagnostic performance between the 15-minute and the 30-minute challenges.
5. To assess the effect of ultrafiltration challenges on other hemodynamic parameters (absolute values and relative changes from baseline): central venous pressure (CVP), heart rate (HR), mean arterial pressure (MAP), pulse pressure, extravascular lung water (EVLW), pulmonary vascular permeability index (PVPI) and global end-diastolic volume index (GEDVi)
6. To evaluate the ability of ultrafiltration challenges to predict hemodynamic instability with preload dependence within 8 hours after the test.

STUDY DESIGN / METHODOLOGY

Type of Research

- Pilot study
- Physiological, prospective, single-center, open-label
- Sequential crossover design with randomization of challenges' order
- Diagnostic test evaluation

Study Population

Inclusion Criteria

- Adults ≥ 18 years hospitalized in the ICU
- Mechanical ventilation and sedation
- Acute kidney injury KDIGO stage 3
- CRRT initiated < 14 days before inclusion
- With a calibrated continuous cardiac index monitoring device in place (PiCCO®, Pulsion Medical, Feldkirch, Germany)

- Informed consent (patient or representative)

Exclusion Criteria

- Arterial lactate > 4 mmol/L
- Calibrated cardiac index < 2 or > 4 L/min/m²
- Preload dependence identified within the preceding 2 hours
- ECMO
- Acute hemorrhage
- End stage chronic kidney disease or renal graft recipient
- Acute stroke with coma
- Fulminant hepatitis
- Inability to perform PLR: amputation, inferior vena cava obstruction, abdominal compartment syndrome
- Pregnancy or breastfeeding
- Imminent death
- Decision of withholding of care
- Patients under legal protection (guardianship, trusteeship, detention)
- Already included in the study

Number of Patients

- 20 patients included

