4. Comparison of diagnostic performance between the 15-minute and 30-minute challenges ROC AUCs compared using DeLong's test.
5. Analysis of additional hemodynamic parameters: CVP, HR, MAP, Pulse pressure, EVLW, PVPI and GEDVi (absolute values and relative changes, correlated with cardiac index variation).

6. Incidence of hemodynamic instability within 8 hours post-test (tachycardia, hypotension, decreased CI, mottling).

Study duration

- Inclusion period: 18 months
- Maximum participation per patient: 72 hours
- Total study duration: 18 months + 3 days

Sample size

- 20 patients planned.
- Each undergoes 2 ultrafiltration challenges (15- and 30-minute, randomized).
- Total: 40 evaluable ultrafiltration challenges.

The sample size was chosen pragmatically, consistent with the pilot/exploratory nature of the study.

STUDY PROCEDURES AND CONDUCT

Overall Study Flow

1. Screening and Inclusion
 - Verify inclusion and exclusion criteria.
 - Provide information to patient or legally authorized representative; obtain consent in compliance with French law.
2. Baseline Assessment
 - Collect demographics and clinical data (age, sex, weight, height, SAPS II, SOFA, reason for ICU admission, history).
 - Record renal data (CRRT indication and parameters, time since CRRT initiation).
 - Baseline hemodynamic measurements: CI, CVP, HR, MAP, PP, EVLW, PVPI, GEDVi, vasopressor dosage
 - Mechanical ventilation settings
3. Randomization
 - Determine challenge sequence (15 vs 30 minutes) using sealed envelopes.
4. Pre-test postural maneuver
 - Passive leg raise (supine) or Trendelenburg (prone).
 - Record hemodynamic parameters before and during maneuver.
5. Ultrafiltration Challenge
 - Remove 250 mL with UF over 15 or 30 minutes.
 - Monitor CI and hemodynamic parameters continuously.
 - Record parameters at the end of challenge.
6. Post-test Postural Maneuver (Reference)
 - Repeat maneuver (PLR or Trendelenburg).
 - Record hemodynamic parameters before and during maneuver.
7. Follow-up
 - Any hemodynamic instability episodes occurring over the following 8h

8. Second Ultrafiltration Challenge

- After a 24h wash-out period, repeat procedure with the alternate duration (30 or 15 minutes).
- Same sequence: pre-test maneuver → challenge → post-test maneuver.

9. Follow-up

- Monitor for 8 hours post-challenges.
- Record any hemodynamic instability.

Data Management

- Data recorded in a secure **electronic case report form (eCRF)**.

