STATISTICAL ANALYSIS

General Principles

- Analyses performed using R software (latest version available).
- Two-sided significance level set at 0.05.
- 95% confidence intervals reported.
- Analyses conducted on the intention-to-treat and per-protocol population (patients with at least one evaluable ultrafiltration challenge).

Primary Analysis

- The primary endpoint is the diagnostic performance of the ultrafiltration challenge (15- and 30-minute tests pooled).
- Performance assessed by calculating the area under the ROC curve (AUC) of cardiac index variation compared with the post-test postural maneuver.
- AUC values will be reported with 95% confidence intervals.

Secondary Analyses

1. Diagnostic performance of the 15-minute and 30-minute ultrafiltration challenge alone (ROC AUC).
2. Determination of the optimal threshold of cardiac index variation (Youden index) defining preload dependence, with sensitivity, specificity, PPV, and NPV.
3. Comparative diagnostic performance of ultrafiltration challenges (pooled and separate) versus the pre-test postural maneuver, compared using the

respective ROC AUCs of 15-minute and 30-minute challenges using DeLong's test.

4. Analysis of additional hemodynamic parameters (CVP, HR, MAP, PP, EVLW, PVPI, GEDVi) in absolute values and relative changes from baseline, correlated with cardiac index variation using Pearson or Spearman correlation.
5. Description of the incidence of hemodynamic instability within 8 hours post-test, expressed as proportions with 95% confidence intervals.

Handling of Missing Data

- Missing data will not be imputed.
- Analyses will be based on available data.
- The extent and reasons for missing data will be described.

Interim Analysis

No interim analysis is planned.

QUALITY ASSURANCE, ETHICS, AND DATA MANAGEMENT

Regulatory and Ethical Aspects

- The study will be conducted in compliance with the Declaration of Helsinki (2013 version) and the principles of Good Clinical Practice (ICH E6 R2).
- The protocol, patient information, and consent form have been submitted to and approved by the CPP Sud-Est VI (Comité de Protection des Personnes).
- The study has been declared to the CNIL (Commission Nationale de l'Informatique et des Libertés) in accordance with French law and the General Data Protection Regulation (GDPR, EU 2016/679).

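### Secondary objective 5 asks for the effect of the challenges on hemodynamics, but the only method named is a correlation, which neither estimates a mean change nor accounts for two challenges per patient

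*Combined protocol and SAP*

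**What the plan says.** Objective 5 (RESEARCH OBJECTIVES, Secondary Objectives) reads: "To assess the effect of ultrafiltration challenges on other hemodynamic parameters (absolute values and relative changes from baseline", followed by the seven parameters. The matching analysis is item 4 of Secondary Analyses. It takes the same parameters as absolute values and as "relative changes from baseline, correlated with cardiac index variation using Pearson or Spearman correlation". Secondary endpoint 5 says the same without naming the coefficient. No other method is given for this objective.

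The design is a crossover in randomised order: "20 patients planned", "Each undergoes 2 ultrafiltration challenges (15- and 30-minute, randomized", "Total: 40 evaluable ultrafiltration challenges". The reason for having two rates is given under Justification of Methodological Choices: "Two rates (15 vs. 30 minutes) tested to assess the effect of ultrafiltration kinetics and plasma refilling". The planned comparison of the two durations is of their ROC AUCs by DeLong's test (secondary endpoint 4; Secondary Analyses, item 3).

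General Principles add "Two-sided significance level set at 0.05" and 95% confidence intervals. Under Data Collected, cardiac index and all seven parameters are recorded before and after each step.

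**The concern.** The question and the method do not match. An effect of a challenge is a mean before-to-after change. A correlation with cardiac index variation describes whether patients whose index falls more also show a larger change in, say, CVP. That is a different question.

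Three consequences follow.

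- **No estimator for the effect.** The plan does not say how the mean change in each parameter will be estimated or what interval will accompany it.
- **No within-patient contrast of the rates.** The two rates were chosen to study kinetics and plasma refilling, and each patient receives both. Yet no analysis compares the size of the response between rates within patient, and no period term appears.
- **No handling of repeated measures.** Two challenges from one patient are not independent observations. If all 40 enter one simple correlation, its p-value may be too small.

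At stake are the physiological effect sizes, which are among the more useful things a pilot can hand to a later trial, and the credibility of any significant correlation.

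**Working it through.** **Inputs from the documents.** 20 patients, 2 challenges each, alpha 0.05 two-sided. The plan's own count reproduces: 20 × 2 = 40. There is no power figure to reproduce, since "The sample size was chosen pragmatically, consistent with the pilot/exploratory nature of the study".

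**Assumptions.** The documents give no within-patient correlation (ICC) for any variable. ICCs from 0 to 0.9 are assumed, with normal data.

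**Step 1: what a correlation can show.** corr(X, Y + c) = corr(X, Y) for any constant c. In a generated set of 40 pairs, adding 10 to every Y left the coefficient at 0.258. A mean fall of any size in MAP or CVP therefore leaves item 4's coefficient unchanged.

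**Step 2: does the AUC comparison cover the rate question?** An AUC depends only on ranks. If one rate lowered cardiac index by a further constant amount in every patient, its AUC could be the same as the other's. The DeLong comparison answers which duration discriminates better, not which produces the larger response.

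**Step 3: type I error if the 40 challenges are pooled.** With no true association, var(r) is approximately (1 + ICCx × ICCy)/40. The nominal test then rejects with probability of about 2 × [1 − Φ(1.96/√(1 + ICCx × ICCy))]. At 0.5/0.5, the inflation factor is 1 + 0.25 = 1.25, the effective n is 40/1.25 = 32, and the rejection rate is 2 × [1 − Φ(1.753)] = 8.0%. Simulation with 40,000 runs:

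| ICC, parameter / cardiac index change | Inflation factor | Approximation | Simulated, pooled Pearson | Simulated, one duration only (n = 20) |
|---|---|---|---|---|
| 0 / 0 | 1.00 | 5.0% | 4.8% | 5.0% |
| 0.3 / 0 | 1.00 | 5.0% | 5.1% | 5.0% |
| 0.3 / 0.3 | 1.09 | 6.0% | 5.8% | 5.0% |
| 0.5 / 0.5 | 1.25 | 8.0% | 7.8% | 5.0% |
| 0.7 / 0.7 | 1.49 | 10.8% | 11.4% | 5.2% |
| 0.9 / 0.5 | 1.45 | 10.4% | 10.4% | 5.0% |
| 0.9 / 0.9 | 1.81 | 14.5% | 15.6% | 5.0% |

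Spearman behaves similarly (4.9% to 14.9%). A separate simulation of 20,000 runs gave 7.9% at 0.5/0.5. Inflation needs both pooling and positive within-patient correlation in both variables.

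**Step 4: a shift between durations.** If both variables differ in mean between the two durations, pooling creates association where none exists within a duration. The obvious remedy, a repeated-measures correlation, is worse unless duration is in the model:

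| Scenario, no association within duration | Pooled Pearson | Repeated-measures correlation, no duration term | Adjusted for duration |
|---|---|---|---|
| Shift 0.5 SD, ICC 0.5 | 8.8% | 14% | 5% |
| Shift 1 SD, ICC 0.5 | 26% | 70% | 5% |
| Shift 1 SD, ICC 0 | 24% | 32% | 5% |

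**Step 5: what a direct estimate would deliver.** The 95% CI half-width for a mean change within one duration is t(0.975, 19)/√20 = 2.093/4.472 = 0.47 SD of the change. For the mean over both durations with patient as cluster, it is 2.093 × √((1 + ICC)/40), which is 0.33 SD at ICC 0 and 0.43 SD at ICC 0.7. The estimates would be coarse but usable for planning.

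**The case against.** Four objections deserve an answer.

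*Pooling is not stated.* A reader might infer that item 4 pools all 40 challenges, and hence that its p-values are anticonservative. The text does not establish this. Pooling is written for the ROC analyses and not for objective 5 or item 4, and per-duration correlations hold 5% at every ICC tried. Even under pooling, the lower end of the range is plausible: each relative change is taken from that challenge's own baseline, and the challenges are 24 hours apart. This objection stands, so the inflation is conditional.

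*Some estimate is implied.* A reader might also conclude that the effect will not be estimated at all. Item 4 does cover absolute values and relative changes, and 95% intervals are a general principle, so a descriptive summary of change is probably intended. This stands in part: what is missing is the named estimator and its handling of paired challenges.

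*The rates are compared on the outcome that the study targets.* No listed objective asks for a 15-versus-30-minute difference in mean response; that aim appears only in the rationale for the design. This is fair. The contrast would serve the plan's stated reason for testing two rates rather than repair an objective that is formally unmet.

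*It is a pilot.* No primary result or diagnostic threshold depends on this analysis. That limits the severity but does not remove the mismatch.

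**Conclusion.** The point holds as a mismatch between objective and method. Correlation is the only technique named for objective 5. It cannot measure a mean change, and it is specified without regard to pairing or randomised order. This part rests on the text alone and needs no assumption.

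The effect on false positives is conditional. If the 40 challenges are pooled and both variables correlate within patient, the type I error at nominal 5% runs from about 5% to 16% over assumed ICCs of 0 to 0.9, and is about 8% at 0.5 in both. It can be higher if both variables also shift between durations. It is absent if either ICC is 0 (without such a shift) or if the durations are analysed separately. The documents do not support the flat statements that the p-values are anticonservative or that no effect will be estimated.

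Severity is modest: the change is worth making, but the primary analysis does not hang on it.

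**What to change.** Rewrite item 4 of Secondary Analyses in two parts.

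1. **Effect.** For cardiac index and each of the seven parameters, fit a linear mixed model of the before-to-after change with duration and period as fixed effects and patient as random effect. Report the mean change by duration and the 15-minus-30-minute difference, each with a 95% CI.
2. **Association.** Replace the simple correlation with a patient-clustered or within-patient correlation, or a mixed-model slope, adjusted for duration. The adjustment is essential, given the 14% to 70% rejection rates without it. If a Pearson/Spearman choice remains, state the rule for it in advance. Label these results exploratory: seven parameters on two scales give 14 tests, and if they were independent the chance of at least one false positive would be 1 − 0.95^14 = 51%.

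The cost is SAP wording and a little more programming. No new data or patients are needed, because the before and after values are already collected.

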To assess the diagnostic performance of a rapid ultrafiltration test (without distinguishing between 15- and 30-minute trials) in detecting preload dependence in critically ill patients treated with continuous renal replacement therapy, by quantifying the change in cardiac index induced by the test and comparing it to that induced by a postural maneuver (reference standard) performed after the ultrafiltration test.

Secondary Objectives

- To assess the diagnostic performance of the 15-minute and 30-minute rapid ultrafiltration tests, respectively, using the same methodology.
- To determine the optimal threshold of cardiac index variation that defines preload dependence for each test (pooled and separately), with calculation of sensitivity, specificity, positive and negative predictive values.
- To compare the diagnostic performance of ultrafiltration tests (pooled and separate) with that of the pre-test postural maneuver.
- To compare the diagnostic performance between the 15-minute and 30-minute tests.
- To evaluate the impact of ultrafiltration tests on additional hemodynamic variables (absolute values and relative changes from baseline): central venous pressure, heart rate, mean and pulse arterial pressure, extravascular lung

water, pulmonary vascular permeability index, and global end-diastolic volume index.

- To assess the ability of ultrafiltration tests (pooled and separate) to predict hemodynamic instability with preload dependence occurring within 8 hours following the test.

Methodology / Study Design

- Pilot study
- Physiological, prospective, single-center, open-label
- Sequential crossover design with sealed-envelope randomization of intervention order
- Diagnostic test evaluation (rapid ultrafiltration challenge)

Primary Endpoint

Diagnostic performance of a rapid ultrafiltration test (regardless of duration), assessed by the area under the ROC curve (receiver operating characteristics) of cardiac index variation compared to the reference measurement (postural maneuver performed after the test).

Secondary Endpoints

- Diagnostic performance of the 15-minute and 30-minute rapid ultrafiltration tests, assessed by ROC analysis of cardiac index variation and comparison with the reference maneuver.
- Optimal thresholds (and 95% CI) of cardiac index variation for each test, determined using the Youden index, with associated sensitivity, specificity, PPV, and NPV.

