- Comparative diagnostic performance of ultrafiltration tests (pooled and separate) versus pre-test postural maneuver, and between tests (15 vs. 30 minutes).
- ROC AUC values compared using DeLong's method.
- Hemodynamic variables measured by cardiac output monitoring (CVP, HR, MAP, pulse pressure, EVLW, PVPI, GEDVi), analyzed as absolute values and changes from baseline, correlated with cardiac index variation.
- Incidence of hemodynamic instability (tachycardia, hypotension, decreased cardiac index, mottling) within 8 hours after the ultrafiltration test.

Target Population

Adult ICU patients (under mechanical ventilation and sedation) with acute kidney injury (KDIGO stage 3) requiring continuous renal replacement therapy initiated within the past 14 days.

Sample Size

N = 20 evaluable patients, each undergoing 2 tests → total of 40 rapid ultrafiltration challenges.

Study Duration

- Inclusion period: 18 months
- Maximum participation per patient: 72 hours
- Total study duration: 18 months + 3 days

Expected Outcomes

The current reference dynamic test (passive leg raise or Trendelenburg) remains imperfect in assessing tolerance to fluid removal during CRRT, with sensitivity <80%. The UF challenge may prove more sensitive, particularly in patients at the borderline between the ascending and plateau phases of the Frank-Starling curve. This simple, dynamic, low-cost test could help clinicians individualize ultrafiltration prescriptions, avoid deleterious hypotension, and rapidly integrate into clinical practice. Currently, no specific dynamic test exists to evaluate the safety and efficacy of fluid removal in this population.

GENERAL INFORMATION

Title: Diagnostic performance of a rapid ultrafiltration test to assess preload dependence in critically ill patients treated with continuous renal replacement therapy.

Project Identifiers and Update History

- Sponsor Code: 69HCL21_1250
- ClinicalTrials.gov registration number: NCT05214729
- CPP Sud-Est VI favorable opinion date: XX/XX/XXXX

Version History

Version	Date	Reason for Update
1	02/11/2021	Initial draft
2	16/03/2022	Comments from CPP

Sponsor

Identity: Hospices Civils de Lyon

[name]

[name] [name]

Signature of the protocol on behalf of the Sponsor:

[name], Director of Health Research

Hospices Civils de Lyon, Health Research Directorate,

Administrative Headquarters,

[name],

[name],

[name]

[contact]

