- Each patient undergoes 2 ultrafiltration challenges (15- and 30-minute, in randomized order)
- Total: 40 evaluable challenges

Randomization

- Randomized order determined by sealed envelope method
- Each patient serves as their own control

Blinding

- Not feasible given the study design

Co-interventions

Recommendation for not changing any of the following parameters, prescription or settings during the trial's interventions:

- Sedation
- Mechanical ventilation
- Vasopressor and inotrope support
- Fluid bolus therapy or transfusion

Study Procedures

1. Baseline data collection (demographics, clinical scores, renal data, hemodynamics)

2. Calibration of the monitoring device and pre-test postural maneuver (PLR or Trendelenburg) during 1 minute with collection of the relative change in continuous cardiac index
3. Ultrafiltration challenge: 250 mL over 15 or 30 minutes (randomized), by setting a UF flow of 1000 ml/h or 500 ml/h, respectively
4. Re-calibration of the monitoring device and post-test postural maneuver (reference standard, PLR or Trendelenburg) during 1 minute with collection of the relative change in continuous cardiac index
5. Repeat sequence for second challenge after a wash-out period of 24h (cross-over design)
6. Follow-up: monitoring for 8 hours post-test for instability

Data Collected

- Demographics: age, sex, weight, height
- Clinical: history, reason for ICU admission, severity scores (SAPS II, SOFA)
- Renal: CRRT indication and parameters
- Hemodynamics: CI, CVP, HR, MAP, PP, EVLW, PVPI, GEDVi (before/after each step), vasopressor dosage
- Ventilatory settings: VT, PEEP, FiO₂, arterial blood gas results
- Results of the pre and post-test postural maneuvers
- Any severe and non-severe adverse events

ENDPOINTS / EVALUATION CRITERIA

Primary Endpoint

The diagnostic performance of the rapid ultrafiltration challenge (pooled 15- and 30-minute tests).

- Performance assessed by the area under the ROC curve (AUC) of cardiac index variation.
- Reference: continuous cardiac index relative variation induced by the post-test postural maneuver performed after the challenge.

Secondary Endpoints

1. Respective diagnostic performance of the 15-minute and 30-minute challenges (ROC AUC).
2. Determination of the optimal threshold of cardiac index variation (Youden index) with sensitivity, specificity, PPV, and NPV.
3. Comparative performance of challenges (pooled and separate) versus the pre-test postural maneuver.

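### Objective 6 asks whether the challenge predicts 8-hour instability with preload dependence, but the endpoint and analysis only count instability of any kind, so the objective gets no answer

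*Combined protocol and SAP*

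**What the plan says.** All references are to the combined protocol and SAP.

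- **Objective.** Research Objectives, Secondary Objectives, item 6: "To evaluate the ability of ultrafiltration challenges to predict hemodynamic instability with preload dependence within 8 hours after the test". The Summary has the same aim, for tests pooled and separate: "to predict hemodynamic instability with preload dependence occurring within 8 hours following the test".
- **Endpoint.** Endpoints / Evaluation Criteria, Secondary Endpoints, item 6: "Incidence of hemodynamic instability within 8 hours post-test (tachycardia, hypotension, decreased CI, mottling". The Summary agrees: "Incidence of hemodynamic instability (tachycardia, hypotension, decreased cardiac index, mottling) within 8 hours after the ultrafiltration test".
- **Analysis.** Statistical Analysis, Secondary Analyses, item 5: "Description of the incidence of hemodynamic instability within 8 hours post-test, expressed as proportions with 95% confidence intervals".
- **Index test.** Primary Endpoint: "Performance assessed by the area under the ROC curve (AUC) of cardiac index variation", that is, the change produced by the 15- or 30-minute challenge.
- **Follow-up.** Overall Study Flow, step 7, placed after the post-test manoeuvre: "Any hemodynamic instability episodes occurring over the following 8h".
- **Preload status.** Data Collected lists the results of the pre-test and post-test manoeuvres and no others.

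**The concern.** Two things are lost between objective and analysis. Prediction becomes a count, and the restriction to preload-dependent episodes disappears. An incidence does not depend on which challenges were positive, so it carries no information about prediction. The restriction is not cosmetic: the Background states that instability during CRRT is not necessarily linked to preload dependence.

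If the gap is left, the link between test and outcome may be examined after the fact with choices made once the data are seen. Such an analysis would meet a second problem. Decreased cardiac index is one of four outcome components, and the endpoint gives it neither a baseline nor a threshold. A fall produced by the challenge and still present when it ends could then be counted as an event, and the test would partly predict itself.

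**Working it through.** **1. Does any planned analysis link the test to the 8-hour outcome?** The five Secondary Analyses are:

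- Item 1: AUC by duration, for preload dependence.
- Item 2: Youden cut-off for preload dependence.
- Item 3: comparison of AUCs, including with the pre-test manoeuvre.
- Item 4: correlation of other hemodynamic variables with cardiac index variation.
- Item 5: incidence of instability.

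None uses instability as the outcome of a prediction.

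**2. What item 5 would yield.** The plan's denominator reproduces: 20 patients × 2 challenges = 40. The documents give no event rate, so the counts below are assumptions. Exact (Clopper-Pearson) 95% intervals, treating challenges as independent:

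| Events in 40 | Proportion | 95% interval |
|---|---|---|
| 4 | 10% | 2.8% to 23.7% |
| 8 | 20% | 9.1% to 35.6% |
| 12 | 30% | 16.6% to 46.5% |

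Each interval is the same whether the challenge separates events from non-events perfectly or not at all.

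**3. What a prediction analysis could yield.** Hanley-McNeil variance, with n1 events, n0 non-events and A the AUC:

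SE² = [A(1−A) + (n1−1)(a−A²) + (n0−1)(b−A²)] / (n1·n0), where a = A/(2−A) and b = 2A²/(1+A).

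At an assumed A = 0.75: a = 0.600, b = 0.6429, A² = 0.5625.

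- 4 events, 36 non-events: (0.1875 + 0.1125 + 2.8125)/144 = 0.02161; SE 0.147; half-width 1.96 × 0.147 = 0.29 (lower limit 0.46).
- 8 and 32: (0.1875 + 0.2625 + 2.4911)/256 = 0.01149; SE 0.107; half-width 0.21 (lower limit 0.54).
- 12 and 28: (0.1875 + 0.4125 + 2.1696)/336 = 0.00824; SE 0.091; half-width 0.18 (lower limit 0.57).

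Clustering: with two challenges per patient and an assumed ICC of 0.5, the design effect is 1 + (2−1) × 0.5 = 1.5. For 8 events the half-width becomes 0.21 × √1.5 = 0.26, with lower limit 0.49.

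One duration alone, with 4 events in 20: (0.1875 + 0.1125 + 1.2054)/64 = 0.02352; SE 0.153; half-width 0.30.

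**4. Overlap of predictor and outcome.** Suppose a share f of events are cardiac index falls carried over from the challenge and ranked perfectly by it. Then apparent AUC = (1−f) × AUC of the other events + f × 1.

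- Other events unrelated to the test (0.50): f = 0.25 gives 0.625, and f = 0.50 gives 0.75.
- Other events at 0.70: f = 0.25 gives 0.775, and f = 0.50 gives 0.85.

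The values of f are illustrative.

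**5. Re-basing does not cure the overlap.** If decreased cardiac index is measured from the end-of-challenge value, the predictor is (end − before) and the outcome is (later − end). With independent errors of equal variance σ², the covariance is −σ² and each variance is 2σ², so error alone gives a correlation of −0.5. Measured from the pre-challenge value, the same arithmetic gives +0.5.

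**The case against.** The strongest reply is about proportion. This is the last of six secondary objectives in a pilot whose size was chosen pragmatically, and restating the objective as descriptive would remove the mismatch at no cost. That stands as to weight, but as the plan now reads the aim is predictive in both places where it is stated.

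The reply is also right about three stronger readings that a reader might be tempted to draw:

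- **That the outcome is the index test itself.** It is not. The test is the change during the challenge. Decreased cardiac index is one of four components, sought in the following 8 hours. What the documents support is a possible overlap, because baseline and threshold are missing.
- **That the planned analysis suffers incorporation bias.** It compares no test with any outcome, so there is nothing to bias. The risk belongs to a prediction analysis that is not yet planned.
- **That the 8-hour outcome is the only one free of a postural manoeuvre, or the only one able to support the hypothesis.** Secondary endpoint 5 covers hemodynamic variables not defined by a manoeuvre. The primary analysis uses a manoeuvre after the challenge in patients without preload dependence identified in the preceding 2 hours, which bears on transition to preload dependence. The expectation that "A UF challenge may have higher diagnostic performance than the passive leg raising test" concerns identifying patients at that transition, and a comparison with the pre-test manoeuvre is planned.

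Finally, an AUC for any instability does not fully answer an objective restricted to preload-dependent instability. That also stands, and the wording of the objective has to reflect it.

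**Conclusion.** The mismatch is real and can be read directly from the text: followed exactly, the plan gives no estimate for objective 6, and it has no means of establishing preload dependence at an episode. It should be corrected, though it touches only a secondary objective.

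A prediction estimate is feasible but imprecise. The half-widths of roughly 0.18 to 0.29 rest on an assumed AUC of 0.75, 4 to 12 assumed events and independent challenges. With few events or appreciable clustering the interval includes 0.5, so the result can only be exploratory. The overlap through decreased cardiac index is a conditional risk to that added analysis. Its size depends on an unknown share of carried-over falls.

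**What to change.** 1. **Analysis.** Keep the incidence as description. Add to item 5 the AUC, with sensitivity and specificity at the chosen cut-off, of the cardiac index change during the challenge (pooled and by duration) and of the pre-test manoeuvre, for instability within 8 hours. Use bootstrap intervals that resample patients, and label the results exploratory.
2. **Window.** Count only episodes that begin after the post-test manoeuvre. The adverse-event window opens at the start of the challenge and should not supply this outcome.
3. **Cardiac index component.** Make the version without decreased cardiac index the main one, and show the version with it as a sensitivity analysis. Do not use the end-of-challenge value as its baseline.
4. **Definitions.** The sponsor should define each component in advance. The figures under Measures for Participant Safety are examples for stopping a challenge, not endpoint definitions. Record onset time and component of each episode in the eCRF.
5. **Objective.** State that the analysis addresses any instability. Analyse the part about preload dependence only in episodes where a manoeuvre was done in routine care. Otherwise reword objective 6 to match the data.

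The cost is revised SAP and endpoint wording, a few eCRF fields, and a wide interval to report. No added patients or study procedures are needed.
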